## 13.0 STUDY MANAGEMENT

### 13.1 Registration Procedures

All patients must be registered with the Cancer Clinical Trials Office before enrollment to study. Prior to registration, eligibility criteria must be confirmed with the Research Staff. To register a patient, call CCTO Monday through Friday, 8:00AM-4:30PM.

### 13.2 Data Management

**13.3 Data must be submitted according to protocol requirements for ALL subjects registered, whether or not study procedures are performed. For screen failures, only the eligibility criteria case report form will be completed. Data obtained during the study will be collected at each subject visit and entered into the protocol database. Subjects will be registered in RPRS, a cancer Biomedical Informatics Grid (caBIG®, NCI) application. Data will be entered into OpenClinica through electronic web-based case report forms (CRFs). OpenClinica is a secure open source system for electronic data capture and clinical data management. All information in OpenClinica will be coded with a unique identifier and will be stored in the database indefinitely. In the event that a subject fails screening, only the eligibility criteria case report form will be completed. The Principal Investigator will carefully monitor study procedures to protect the safety of research subjects, the quality of the data and integrity of the study. Monitoring and Auditing**

#### 13.3.1 Medical Monitor:

The Medical Monitor, Principal Investigators and study staff will meet to review safety data after each of the Data Monitor periodic visit.

#### 13.3.2 Data Monitor:

UAMS is the Sponsor. One (or more) Data Monitor(s) will be appointed by the monitoring division of the UAMS Office of Research regulatory Affairs (ORRA) to assure that the rights and well-being of human subjects are protected, that the data are accurate, complete and verifiable from source documents and that the trial is conducted in compliance with currently approved protocol/amendments, with GCP, and with the applicable regulatory requirements set forth in 21 CFR 312.

The Data Monitor(s) will be familiar with the protocol, the informed consent form, any other information provided to the subjects, SOPs, GCP and applicable regulatory requirements.

Data Monitor(s) will have access to research subjects' medical records and other study-related records. The investigator agrees to cooperate with the study coordinator and Medical Monitor to ensure that any problems detected in the course of these monitoring visits are resolved. Personal contact between the Data Monitor, Medical Monitor, study staff and the investigator will be maintained throughout the clinical trial to assure that the investigator is fulfilling his/her obligations and that the facilities used in the clinical trial remain acceptable.

#### 13.3.3 Research Subject Safety and Stopping Rules:

If 2 SAEs occur with attribution to the study, the trial will be suspended until further review is completed by the Medical Monitor, PI, sponsor and FDA. This will be accomplished by the

study team, the PI, Co-PI, biostatistician, Medical Monitor and CRA, either at the regular meeting or a special meeting called by the Medical Monitor or the PI because of the SAEs.

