Spatially fractionated radiotherapy (GRID) is a technique of irradiation that has been used successfully for the curative or palliative treatment of bulky tumors  $\geq 6$  cm [5-7]. Irradiation is delivered through a specially made grid collimator or by using a multi-leaf collimator (MLC) as a grid field shaper [5, 8-10]. In GRID therapy the target volume does not receive a homogeneous dose of radiation. Only the volume under the open grid areas receives irradiation from the primary beam. Our results [11] have shown that GRID followed by definitive chemoradiation resulted in excellent control of bulky disease (79%) in patients with locally advanced squamous-cell carcinoma of the head and neck. In these patients, acute toxicity profiles were acceptable and were similar to reports of chemotherapy and radiotherapy alone. In addition, no patient has developed a local recurrence in the irradiated GRID volume, but several have developed distant metastatic disease, which is common in this population. Our series also demonstrated that GRID is a feasible and valuable therapeutic option for bulky disease presentation. The therapeutic advantage of GRID therapy has been evaluated. Zwicker [12] et al reported that, for a wide range of tumor radiosensitivities, GRID therapy may have a significant therapeutic advantage over open-field radiotherapy to achieve the same level of tumor-cell kill. Highly radioresistant,

hypoxic cells are often present in bulky untreated tumors, and it is in these cases in which GRID use appears more advantageous.

Based on the above clinical experience, we hypothesize that GRID can be used safely in pediatric patients with osteosarcoma of the extremity, and will show a favorable toxicity profile in this population. However, the toxicity profile of GRID therapy, at any dose level, in pediatric patients is unknown.

Therefore, the purpose of this phase 1 clinical trial is to investigate the toxicity profile of GRID in pediatric osteosarcoma of the extremity.

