## 11.0 ADVERSE EVENTS

### 11.1 Adverse Events Associated with GRID therapy

The potential risks of using a GRID block for radiotherapy delivery are similar to those of radiation therapy using a standard multi-leaf collimator (MLC). The risks are not due to the use of the GRID block itself, but from the actual irradiation as is the case in standard MLC radiotherapy.

Risks and side effects related to GRID therapy include:

Likely:

- Skin reaction (redness)
- Hair loss in the treated area

Less Likely:

- Fatigue
- Reductions in blood counts
- Treatment of large tumors with radiation, chemotherapy and surgery may results in infection or lack of healing which could result in prolonged hospitalization.

Rare:

- Fibrosis (hardening of the tissues)
- Pain in the treated limb
- Swelling
- Fracture of bone
- Bruising of skin
- Neve damage
- Amputation

There exists the potential risk for loss of confidentiality. Measures to protect the confidentiality of study participants will be implemented as described in the Data Handling and Recordkeeping section.

There will be no direct benefits to the study participants; however, knowledge gained from the study could potentially benefits patients in the future.

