### 11.3.3 Serious Adverse Events

A “serious” adverse event is defined in regulatory terminology as any untoward medical occurrence that:

- Results in death.
  - If death results from (progression of) the disease, the disease should be reported as event (SAE) itself.
- Is life-threatening.
  - The patient was at risk of death at the time of the event; it does not refer to an event that hypothetically might have caused death if it were more severe.
- Requires in-patient hospitalization or prolongation of existing hospitalization for  $\geq 24$  hours.
- Results in persistent or significant disability or incapacity.
- Is a congenital anomaly/birth defect.
- Is an important medical event.

Any event that does not meet the above criteria, but that in the judgment of the investigator jeopardizes the patient, may be considered for reporting as a serious adverse event. The event may require medical or surgical intervention to prevent one of the outcomes listed in the definition of “Serious Adverse Event”.

For example: allergic bronchospasm requiring intensive treatment in an emergency room or at home; convulsions that may not result in hospitalization; development of drug abuse or drug dependency.

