## 12.0 STATISTICAL CONSIDERATIONS

### 12.1 Study Design/Study Endpoints

- This is a dose-escalation study with three radiation doses: 10Gy, 15Gy, and 20Gy. It uses the traditional “3+3” design to determine whether to escalate or de-escalate doses, and thereby to determine the maximum tolerated dose (MTD) on this protocol. The initial cohort of subjects will receive a 15Gy dose of GRID therapy, as shown in the diagram. The second cohort of subjects will receive either 20Gy or 10Gy of GRID, also as shown in the diagram.
- The study endpoint is dose-limiting toxicity (DLT), which is defined as a treatment-related AE of Grade 3 or higher. Subjects will be assessed at both their 30-day post-surgery visit and their 90-day post-surgery visit for presence of a DLT.

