## 12.2 Evaluation Plan

- **Table 1** shows how the number of DLTs in the initial cohort will be used to determine whether to escalate or de-escalate the GRID dose in the next cohort.

Table 1: Toxicity Decision Rules for Initial Cohort (GRID at 15Gy)	
DLTs/ Cohort	Action
0/3	Begin accrual to Escalation Cohort
1/3	Expand Initial Cohort to 6 subjects
1/6	Begin accrual to Escalation Cohort
2/6, 3/6, or 4/6	Begin Accrual to De-Escalation Cohort
2/3 or 3/3	Begin Accrual to De-Escalation Cohort

 DLT = Dose-Limiting Toxicity

- If the second cohort is the Escalation cohort, then **Table 2** shows how the number of DLTs will be used to determine the MTD on this protocol.

Table 2: Toxicity Decision Rules for Escalation Cohort (GRID at 20Gy)	
DLTs/ Cohort	Action
0/3 or 1/3	Expand cohort to 6 subjects
0/6 or 1/6	Stop: Declare escalation dose to be the MTD 
2/6, 3/6, or 4/6	Stop: Previous dose level is the MTD 
2/3 or 3/3	Stop: Previous dose level is the MTD 

 DLT = Dose-Limiting Toxicity

 MTD = Maximum Tolerated Dose

- On the other hand, if the second cohort is the De-Escalation cohort, then **Table 3** shows how the number of DLTs will be used to determine whether 10Gy is at or above the MTD on this protocol.

Table 3: Toxicity Decision Rules for De-Escalation Cohort (GRID at 10Gy)	
DLTs/ Cohort	Action
0/3 or 1/3	Expand cohort to 6 subjects.
0/6 or 1/6	Stop: De-escalation dose level is the MTD 
2/6, 3/6, or 4/6	Stop: De-escalation dose level is above MTD 
2/3 or 3/3	Stop: De-escalation dose level is above MTD 

 DLT = Dose-Limiting Toxicity

 MTD = Maximum Tolerated Dose

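### Section 13.3.3 suspends the trial only at the second attributed SAE, so a lone treatment-related death or GRID-attributed amputation at 15Gy triggers no mandatory pause and can still lead to 20Gy

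*Combined protocol and SAP*

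**What the plan says.** The suspension rule in 13.3.3 reads: "If 2 SAEs occur with attribution to the study, the trial will be suspended until further review is completed". It counts SAEs and makes no distinction by severity.

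Section 12.1 defines the endpoint, DLT, "which is defined as a treatment-related AE of Grade 3 or higher". Every related event from Grade 3 to death therefore adds one to the count, and that count is all that the tables in 12.2 use. The first cohort receives 15Gy, the middle of three doses. At 1/3, Table 1 says "Expand Initial Cohort to 6 subjects"; at 1/6 it says "Begin accrual to Escalation Cohort", which is the 20Gy cohort. At 20Gy, Table 2 also expands after 1/3, and at 1/6 it says "Stop: Declare escalation dose to be the MTD".

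Other oversight text:

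- 11.4.1: the PI is told of any SAE within 24 hours, and the IRB of unanticipated problems within 10 business days.
- 11.4.2: other adverse events go to annual IRB continuing review.
- 13.3.1: the Medical Monitor, PIs and staff review safety data after each Data Monitor visit; no interval is given.
- 8.3: toxicity can lead to removal of an individual patient.
- 13.3.2 and 13.4: general reference to regulations and institutional policy.

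None of these requires GRID to stop before the next subject.

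**The concern.** Section 4.1 states that "the toxicity profile of GRID therapy, at any dose level, in pediatric patients is unknown". Subjects may be as young as 5, and 11.1 expects no direct benefit to them. The same section lists amputation among the rare risks. In this setting one treatment-related death is reason to stop and look before anyone else is irradiated, whatever the DLT fraction.

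The plan does not require that. When the death is the only attributed SAE so far, it uses one of the two SAEs allowed by 13.3.3 and one DLT in Table 1. The dose rules then carry on, possibly to a higher dose. Whether anyone pauses is left to the judgment of the PI, the Medical Monitor or the IRB.

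**Working it through.** **The plan's own figure.** Enumerating every path through Tables 1 to 3 gives possible totals of 6, 9 and 12 subjects, which agrees with the minimum of 6 and maximum of 12 in 12.3.

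**The path.** Only two results at 15Gy lead to 20Gy: 0/3, or 1/3 followed by no DLT in the next three (1/6). The event must therefore fall among the first three subjects. A DLT in subjects 4 to 6 can occur only after 1/3, so it makes at least 2/6 and de-escalates.

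| Step | DLT count | Attributed SAEs | Required action |
|---|---|---|---|
| Related death among the first three at 15Gy | 1/3 | 1 | Expand at 15Gy |
| No DLT in the next three | 1/6 | 1 | Open 20Gy |
| No DLT in six at 20Gy | 0/6 | 1 | 20Gy is the MTD |

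The SAE count stays below 2 throughout. Subjects treated after the 1/3 result: 3 + 6 = 9. If the event is in subject 1 before subjects 2 and 3 are treated: 2 + 3 + 6 = 11.

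**How likely.** The documents give no DLT rates. I assume independent DLTs with probability p = 0.10, 0.20 or 0.30, equal at all doses unless stated; q is an assumed rate of attributed SAEs that are not DLTs.

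| Quantity | Formula | p = 0.10 | p = 0.20 | p = 0.30 |
|---|---|---|---|---|
| Table 1 escalates, given 1/3 | (1−p)³ | 73% | 51% | 34% |
| Same, not suspended, q = 0.05 | (1−p−q)³ | 61% | 42% | 27% |
| Same, not suspended, q = 0.10 | (1−p−q)³ | 51% | 34% | 22% |
| 20Gy then named MTD, no further DLT | (1−p)⁹ | 39% | 13% | 4% |
| 20Gy then named MTD, 0/6 or 1/6 there | (1−p)³ × P(0/6 or 1/6) | 65% | 34% | 14% |

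The last row is an upper end: a second DLT at 20Gy avoids suspension only if it is not an SAE. If the DLT rate at 20Gy is 10 points above that at 15Gy, the last two rows become 19%, 6% and 2%, and up to 48%, 22% and 8%.

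These figures are all conditional on 1/3 at 15Gy. The unconditional chance of 1/3 then 0/3 is 3p(1−p)² × (1−p)³ = 3p(1−p)⁵ = 0.177, 0.197 and 0.151. Let f be the assumed share of DLTs that are a death or GRID-attributed amputation:

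- f = 0.05: 0.9%, 1.0% and 0.8%
- f = 0.10: 1.8%, 2.0% and 1.5%

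So the path from such an event to opening 20Gy has probability of about 0.8% to 2.0%. These are upper limits, because an attributed SAE that is not a DLT would also suspend the trial.

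**The case against.** **Review is not absent.** A reader might infer that the plan requires no review at all after a death. It does not go that far. The meetings in 13.3.1 are mandatory, IRB continuing review is annual, and the PI must be told within 24 hours. What is missing is a pause triggered by the event.

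**A death is not treated like any Grade 3 event in every respect.** That too is tempting to infer, but it holds only for the DLT count. Under 11.3.3 a death is always an SAE, so it brings the 24-hour notice and, if attributed, counts toward 13.3.3. A Grade 3 event that meets no SAE criterion does neither.

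**Amputation is the weaker example.** It counts as a DLT only if attributed to GRID and graded 3 or higher. Because 13.3.3 counts SAEs and not patients, an earlier attributed SAE in the same subject would make the amputation the second. Section 11.1 names "infection or lack of healing which could result in prolonged hospitalization", and 11.3.3 classes as serious an event that "Requires in-patient hospitalization or prolongation of existing hospitalization". The documents do not say whether one worsening course is one SAE or two. The gap is clearest for a death with no prior attributed SAE.

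**Some text cannot be seen.** A figure under 11.4.1, the schema in 2.0 and the diagram cited in 12.1 are not shown, and the IRB policy cited in 11.4.1 and the regulations cited in 13.3.2 are not reproduced. Any of these might require a hold. The statement is therefore limited to the visible text.

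**Rarity and choice.** The path is rare on any assumption used here, and a two-SAE threshold may be deliberate. That argues against ranking the point among the most serious faults. It does not remove the point, since single-event rules exist for rare and irreversible harm.

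**Conclusion.** The concern holds in limited form. In the visible text, a treatment-related death among the first three subjects at 15Gy requires no event-triggered pause when it is the only DLT and the only attributed SAE, and Table 1 can then open 20Gy. The same is true of a GRID-attributed amputation if it is graded 3 or higher and no earlier attributed SAE has occurred.

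That reading of the rules needs no assumed rates; the size does. The path is rare and the figures are upper limits, but up to nine subjects, or eleven if the event comes first, could be treated without a mandatory stop. The sample size of 6 to 12 is correct; the fault is a missing safety rule. The sponsor should make the change, first checking that the unseen figures do not already contain such a hold.

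**What to change.** Amend 13.3.3 as follows:

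- One treatment-related death, or one amputation attributed to GRID, also suspends the trial. Amputation performed as the routine cancer operation does not count.
- Until the review described in 13.3.3 is complete, no subject receives GRID, including those already consented or in an unfinished cohort, and no row of Tables 1 to 3 is acted on.
- Subjects awaiting GRID continue routine chemotherapy and surgery without delay. Anyone who goes to surgery without GRID is not counted for DLT and is replaced.
- If the review allows the trial to resume, it does so under Tables 1 to 3 or at a lower dose.

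The sponsor may also wish to decide whether a single related life-threatening event belongs in the rule.

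**Cost.** A few sentences, using a review group the protocol already names. The decision tables and the maximum of 12 treated subjects stay as they are. The main downside is an occasional extra pause, of unstated length because the FDA takes part in the review, in a study planned for 12 months. Enumerating all paths with each DLT being a death or amputation with probability f, the chance of at least one such event in the trial is 5%, 9% and 14% for f = 0.05, and 9%, 18% and 26% for f = 0.10, at p = 0.10, 0.20 and 0.30. These are upper limits on added pauses, since some events will come after the last GRID treatment or when a two-SAE suspension is already due. Section 6.0 allows 15 consents for 12 subjects, so 15 − 12 = 3 replacements fit if no other consented subject is lost.

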#### **13.4 Ethical Considerations**

This study will be conducted in accordance with all applicable government regulations and University of Arkansas for Medical Sciences research policies and procedures. This protocol and any amendments will be submitted and approved by the UAMS Institutional Review Board (IRB) to conduct the study.

The formal consent of each subject, using the IRB-approved consent form, will be obtained before that subject is submitted to any study procedure. All subjects for this study will be provided a consent form describing this study and providing sufficient information in language suitable for subjects to make an informed decision about their participation in this study. The person obtaining consent will thoroughly explain each element of the document and outline the risks and benefits, alternate treatment(s), and requirements of the study. The consent process will take place in a quiet and private room, and subjects may take as much time as needed to make a decision about their participation. Participation privacy will be maintained and questions regarding participation will be answered. No coercion or undue influence will be used in the consent process. This consent form must be signed by the subject or legally authorized representative (only if applicable), and the individual obtaining the consent. A copy of the signed consent will be given to the participant, and the informed consent process will be documented in each subject's research record. If assent is required, include a statement that assent will be obtained and that assenting minors will be consented if they reach the age of majority during the study (if applicable).

#### **13.5 Dissemination of Data**

Results of this study may be used for presentations, posters, or publications. The publications will not contain any identifiable information that could be linked to a participant.

